7.3. Operational considerations for interim analysis

- This analysis will be performed by an independent data analysis centre (IDAC), in order to maintain the blind to the treatment codes. IDAC members will have access to the unblinded study data and will store their programs in LSAF (Life Science Analytics Framework) in a restricted area, not accessible by the study team until the end of the study.
- The study statistician and the statistical analysts will notify the IDAC when 13 culture-confirmed cases after the 2nd dose will be reached and provide the IDAC with the SAS codes for interim analysis under the anticipated statistical considerations.
- An independent GSK statistician will validate the outcome of the interim analysis provided by IDAC, to check whether efficacy/futility criteria are met. He/she will have access to the same restricted area the IDAC will have access to.
- If the obtained test statistic lies in the "Rejection Region", i.e. its value is higher than the rejection boundary value, it suggests the study meets the efficacy criteria at the interim analysis. If the test statistic lies in the "Continue Region", i.e. its value is between the rejection and acceptance boundaries, it suggests the study should continue, If the obtained test statistic lies in the "Acceptance Region", i.e. its value is lower than the acceptance boundary value, it suggests the study meets the futility criteria at the interim analysis (non binding criteria).

8. CHANGES FROM PLANNED ANALYSES

Not applicable

9. NON-STANDARD DATA DERIVATION RULES AND STATISTICAL METHODS

The following sections describe additional derivation rules and statistical methods which are not presented in section 10.1.

9.1. Data derivation

Not applicable

9.2. Statistical Method

Not applicable

10. ANNEXES

10.1. Business rules for standard data derivations and statistical methods

This section contains GSK Vaccines' standard rules for data display and derivation for clinical and epidemiological studies. These rules will be applied along with those detailed in section 9 (additional study-specific rules) of this document, if any.

10.1.1. Attributing events to vaccine doses

The dose relative to an event is the most recent study dose given to a subject prior to the start of a given event. For example, if the start date of an adverse event is between Dose 1 and Dose 2, the relative dose will be Dose 1.

If an event starts on the same day as a study dose, the relative dose will be derived from the additional information provided in the CRF using the contents of the flag indicating if the event occurred before or after vaccination. If 'after vaccination' is selected, the relative dose for the event will be the one administered on the start day of the event. If 'before vaccination' is selected, the relative dose for the event will be the dose prior to this one. If the flag indicating whether the event occurred before or after vaccination is missing then "after vaccination" is imputed and relative dose is assigned accordingly.

10.1.2. Handling of missing data

10.1.2.1. Dates

When partially completed dates (i.e. with missing day or month) are used in calculations, the following standard rules will be applied:

- A missing day will be replaced by 1
- A missing day and month will be replaced by January 1st

The following exceptions apply:

- Birth dates:
 - A missing day will be replaced by 15
 - A missing month will be replaced by June 30th
- Adverse event start dates with missing day:
 - If the event starts in the same month as at least one of the study doses, the contents of AE.AESTRTPT (the flag indicating if the event occurred before or after vaccination) will be used to complete the date. If 'after vaccination' is selected or the flag is missing, the imputed start date will match the first (or only) study dose given during that month. If 'before vaccination' is selected, the imputed date will be first day of that month.

- Adverse event start dates with missing day and month:
 - If the event starts in the same year as at least one of the study doses, the contents of AE.AESTRTPT (the flag indicating if the event occurred before or after vaccination) will be used to complete the date. If 'after vaccination' is selected or the flag is missing, the imputed start date will match the first (or only) study dose given during that year. If 'before vaccination' is selected, the imputed date will be one day before the first (or only) study dose given during that year.

All other cases of incomplete AE or concomitant medication/vaccination start date will follow the standard rules above.

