5.5. Analysis of safety and reactogenicity

5.5.1. Analysis of safety and reactogenicity planned in the protocol

The primary analysis will be performed on the Solicited Safety and Unsolicited Safety sets.

Table 6 Statistical analysis methods for the primary study objectives

Endpoint	Statistical Analysis Methods
Primary	Within groups assessment
-	The overall incidence, with exact 95% confidence intervals (CIs) of any solicited AE (local or
	general), of at least 1 solicited local AE and of at least 1 solicited general AE during the 7-day
	(Day 1-7) period will be tabulated per study group and for each dose and overall. The same
	calculations will be performed for solicited AEs rated as grade 3 and fever >40°C/104°F.
	The overall incidence, with exact 95% confidence intervals (CIs) of any unsolicited AE,
	unsolicited AEs by MedDRA system organ class and by preferred term during the 30-day (Day
	1-30) follow-up post-vaccination period will be tabulated per study group and after each dose
	and overall. The same calculations will be performed for unsolicited AEs rated as grade 3, for
	unsolicited AEs causally related to vaccination and for grade 3 unsolicited AEs causally related
	to vaccination.
	The number and percentages of subjects who experienced at least one SAE or any pIMD during
	the entire study period (Groups 1-3 Day 1-366, Groups 4 and 5 Day 1-426) will be reported.
	I ne percentage of subjects having naematology and blochemistry results below of above the
	normal laboratory ranges with the changes from the baseline values will be tabulated by time
	point for Group 1 to 4 and Group 5 Step 1.
	Duration will be presented.
	The verbalin reports of unsolicited symptoms will be reviewed by a GSK physician and the
	Tarminology
	Cerieve adverse events and withdrawel due to adverse event(e) will be described in detail
	Serious adverse events and withdrawal due to adverse event(s) will be described in detail.

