10.1.3.7. Duration of events

The duration of an event with a start and end date will be the number of days between the start and end dates plus one day, i.e. an event that starts on 03MAR2018 and ends on 12MAR2018 has a duration of 10 days.

The duration of solicited events will be calculated from the first day of occurrence to last day of occurrence with the adverse event reported at grade 1 or higher during the solicited adverse event period.

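### SAP 10.1.2.1 sets a missing day to 1 without exempting adverse event end dates, so a partial end date gives an impossible or shortened duration

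*SAP*

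**What the plan says.** SAP 10.1.2.1 opens with a rule of general scope: "When partially completed dates (i.e. with missing day or month) are used in calculations, the following standard rules will be applied". Two defaults follow: "A missing day will be replaced by 1" and "A missing day and month will be replaced by January 1st".

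The exceptions are then listed.
- **Birth dates** have their own values, for example "A missing day will be replaced by 15".
- **AE start dates** are handled separately for a missing day ("Adverse event start dates with missing day") and for a missing day and month. If the event falls in the same month or year as a dose, the before/after-vaccination flag decides the date. With 'after', or with no flag, the start becomes the date of the first dose in that month or year.

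The section closes with "All other cases of incomplete AE or concomitant medication/vaccination start date will follow the standard rules above". It has no exception for end dates and does not require an imputed end to fall on or after the start.

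SAP 10.1.3.7 states: "The duration of an event with a start and end date will be the number of days between the start and end dates"; a further day is then added. It illustrates this with 03MAR2018 to 12MAR2018, which gives 10 days. A separate paragraph takes solicited durations from the daily diary grades. SAP Table 6 (section 5.5.1) adds "Duration will be presented" without naming an event type. SAP 9.1, the place for study-specific derivations, reads 'Not applicable'.

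**The concern.** Setting a missing day to the first of the month gives the earliest possible date. For an end date, that produces the shortest possible event and often an end before the start. The SAP gives AE start dates a careful exception but has no counterpart for end dates, and nothing later in the document corrects the result.

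Partial end dates are plausible here. Under protocol 12.5.4, unsolicited AEs that were neither medically attended nor of concern to the subject are collected by interview at the next visit, so some end dates will rest on recall.

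What is at stake is whether any reported durations of unsolicited events are valid. Negative values would be noticed. A positive but shortened value, such as 5 days for a 14-day event, would not.

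**Working it through.** **Inputs.** The default rules and exceptions come from SAP 10.1.2.1. The formula comes from SAP 10.1.3.7: duration = (end date - start date) + 1.

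**The SAP's own example.** 03MAR2018 to 12MAR2018: (12 - 3) + 1 = 10 days, as stated.

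**Same example with the end day missing.** The end becomes 01MAR2018: (1 - 3) + 1 = -1 day.

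**Any event that starts and ends in the same month, end day missing.** For start day s, duration = (1 - s) + 1 = 2 - s.
- s = 1 gives 1 day.
- s = 2 gives 0 days.
- s = 15 gives -13 days.
- s = 31 gives -29 days.

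In a 31-day month there are 31 × 32 / 2 = 496 possible start/end pairs. The rule treats them as follows:

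| Start day | Pairs | Result |
|---|---|---|
| 3 to 31 | 29 + 28 + … + 1 = 435 | negative |
| 2 | 30 | zero |
| 1, true end after the 1st | 30 | shortened to 1 day |
| 1, true end on the 1st | 1 | correct |

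**End in a later month, end day missing.** The shortfall is the true end day minus 1.
- 28 March to 10 April: true duration 14 days; with the end set to 1 April, (1 April - 28 March) + 1 = 5. Shortfall 10 - 1 = 9 days.
- 20FEB2018 to 12MAR2018: true duration 21 days; with the end set to 01MAR2018, 10. Shortfall 12 - 1 = 11 days.

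**End known only by year.** Start 03MAR2018, end 2018: the end becomes 01JAN2018, which is 61 days before the start, so the duration is -61 + 1 = -60 days.

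**Start and end both partial in a dose month.** Suppose the dose was given on 10MAR2018 and the flag is 'after vaccination' or missing. The start moves to 10MAR2018 and the end to 01MAR2018: (1 - 10) + 1 = -8 days. Here the start-date exception and the default work against each other.

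**When the result is right.** Where the start date is known, only if the event truly ended on the imputed day: the 1st of the month, or 1 January when the month is also missing.

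**The case against.** The strongest reply concerns how the section is read. Every AE rule in SAP 10.1.2.1 concerns start dates, and so does the closing sentence. SAP 10.1.3.7 defines duration for an event that has a start and an end date, which could be taken to require a complete end date. On that reading a partial end date gives no duration. The reading is possible, but the opening sentence of SAP 10.1.2.1 covers all partial dates used in calculations, and a programmer following it would apply day 1. Even on the narrower reading the SAP has no stated end-date rule, so the same added sentence is needed.

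The second reply concerns impact, and most of it stands. A reader might infer that the primary safety results are biased. The documents do not support that:
- The primary endpoints are occurrence, intensity, relationship to vaccination and laboratory abnormalities, not duration.
- Table 6 does not say whose duration is presented.
- SAP 5.5.2.2 itemises the unsolicited AE, SAE and pIMD outputs and lists no duration table. The full table list is a separate document (SAP 10.2).

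A reader might also infer an unsafe direction of error in a first-in-human trial. No stated safety decision uses the duration of an unsolicited event. In protocol Table 26 only holding rules 2a and 2b have a duration element (48 hours or more), and both concern solicited AEs.

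Finally, SAP 7.1 says analyses are run on clean data. A duration of -13 days would probably be queried, so the shortened positive values are the likelier ones to survive.

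**Conclusion.** The point holds as a defect in a stated derivation rule. Taken literally, SAP 10.1.2.1 and 10.1.3.7 together give a zero or negative duration when an event starts after the 1st of the month in which it ends. They give a shortened one when it ends in a later month, unless it truly ended on the imputed day. If start and end are both partial in a dose month, the duration can again be negative.

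The reach is small. It covers descriptive durations of unsolicited events, including SAEs and pIMDs, with a partial end date. Solicited durations, AE incidence, dose attribution (which uses start dates, SAP 10.1.1), holding rules and efficacy are unaffected. Whether unsolicited durations will be tabulated at all is an inference from Table 6 and the general formula in SAP 10.1.3.7.

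The size of the effect on any summary is unknown, because the documents give neither the number of partial end dates nor whether the eCRF accepts them. The 435 of 496 above counts calendar possibilities; it is not an expected rate. A reader might also take the average shortfall for later-month endings, (0 + 1 + … + 29) / 30 = 14.5 days, as the expected bias. That figure assumes end days spread evenly over a 30-day month, which nothing in the documents establishes.

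**What to change.** Add one sentence to SAP 10.1.2.1: the standard rules do not apply to end dates, and where an end date is partial the duration is left missing and the partial date is listed.

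If imputation is preferred, use the last day of the month, or of the year when the month is also missing. Cap it at last contact, death or data cut-off, never allow it before the start date, and label the resulting duration an upper bound. This option replaces a downward bias with an upward one: the SAP's 10-day example with its end day missing would become (31 - 3) + 1 = 29 days before any cap. It should not be presented as an unbiased correction.

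The cost is the SAP sentence and a small change to the derivation code. The downside is that some durations will be missing or will be upper bounds.

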10.1.2.2. Laboratory data

Missing laboratory results (including immunological data) will not be replaced.

Haematology/chemistry laboratory data requiring grading as per FDA Toxicity Grading Scale for Healthy Adult and Adolescent Volunteers Enrolled in Preventive Vaccine Clinical Trials may have more decimals than expected or may require conversion to the unit associated to the grade, leading to more decimals than expected.

In order to determine the grading, the following rule will be used

- 1. In case a conversion is needed, the original results will be used for the conversion without a previous rounding.
- 2. In case an approximation is needed to determine the grading, the result (or the result divided by the upper limit of the normal range (ULN), depending on the test) expressed in the expected units will be rounded to the number of decimals used for the grading.

If the original result is expressed as < x or > x, then, for grading purpose, it is imputed to x and converted to expected units, if needed.

10.1.2.3. Daily recording of solicited adverse events

10.1.2.3.1. Studies with electronic diaries

As the study foresees the use of electronic diaries for the collection of solicited adverse events, a solicited adverse event will be considered present only when a daily recording of grade 1 or more is present.

10.1.2.4. Unsolicited adverse events

Unsolicited adverse event summaries are including serious adverse events unless specified otherwise.

Missing severity, relationship with study vaccine, and outcome of unsolicited adverse events will not be replaced and will appear as 'UNKNOWN' in all statistical output.

10.1.3. Data derivation

10.1.3.1. Weight

Weight will be presented in kilograms. Weights reported in pounds will be converted as follows:

Weight in kilograms = Weight in pounds / 2.2

10.1.3.2. Height

Height will be presented in centimeters. Heights reported in feet and inches will be converted as follows:

Height in centimeters = Height in inches x 2.54

10.1.3.3. Body mass index (BMI)

BMI will be calculated as follows:

 $BMI = (Weight in kilograms) / (Height in meters)^2$

10.1.3.4. Temperature

Temperatures will be presented in degrees Celsius (°C). Temperatures reported in degrees Fahrenheit (°F) will be converted as follows:

Temperature (Celsius) = ((Temperature (Fahrenheit) - 32) x 5)/9

10.1.3.5. Numerical serology results

Not applicable

10.1.3.6. Onset day

The onset day for an event (e.g. AE, medication, vaccination) is the number of days between the last study vaccination and the start date of the event. This is 1 for an event occurring on the same day as a vaccination (and reported as starting after vaccination).

10.1.3.7. Duration of events

The duration of an event with a start and end date will be the number of days between the start and end dates plus one day, i.e. an event that starts on 03MAR2018 and ends on 12MAR2018 has a duration of 10 days.

The duration of solicited events will be calculated from the first day of occurrence to last day of occurrence with the adverse event reported at grade 1 or higher during the solicited adverse event period.

10.1.3.8. Counting rules for combining solicited and unsolicited adverse events

Multiple events with the same preferred term which start on the same day are counted as only one occurrence.

10.1.3.9. Counting rules for occurrences of solicited adverse events

When the occurrences of solicited adverse events are summarized, each event recorded as having occurred during a specific period will be counted as only one occurrence regardless of the number of days on which it occurs.

10.1.4. Display of decimals

10.1.4.1. Percentages

Percentages and their corresponding confidence limits will be displayed with:

- no decimals when there are fewer than 50 subjects in each tabulated group
- one decimal when there are at least 50 subjects in at least one tabulated group
 - Exceptions will be made for percentages that are not 0% or 100% but appear as 0% or 100% due to rounding. For these specific cases the number of decimals will be increased until the displayed value is no longer 0% or 100%. Examples are given in the following table.

n/N	Displayed percentage
10/45	22%
1/45	2%
10/55	18.2%
1/55	1.8%
1/300	0.3%
1/3000	0.03%
1/30000	0.003%
299/300	99.7%
2999/3000	99.97%
29999/30000	99.997%

- The display of additional decimals for values close to 0% or 100% will be applied only to point estimates and not confidence limits, which can be rounded and displayed as 0% or 100%.
- Values of exactly 0% or 100% will be presented with no decimals regardless of the number of subjects per tabulated group.

10.1.4.2. Differences in percentages

Differences in percentages and their corresponding confidence limits will be displayed with one more decimal than the maximum number used to display the individual percentages, for example the difference between two percentages displayed with one decimal will be displayed with two decimals.

10.1.4.3. Demographic/baseline characteristics statistics

The mean, median, and standard deviation for continuous baseline characteristics (height, weight, body mass index (BMI), pre-vaccination body temperature) will be presented with one decimal.

The minimum and maximum values and quartile values (if required) will be presented with the same number of decimals as the observed values.

The maxima and minima of transformed height/weight variables will be displayed with no decimals.

The maxima and minima of transformed body temperatures will be displayed with one decimal.

10.1.4.4. Serological summary statistics

Not applicable

10.1.5. Statistical methodology

10.1.5.1. Exact confidence intervals around proportions

The exact confidence intervals around within-group proportions are derived using the method of Clopper and Pearson [Clopper, 1934].

10.1.5.2. Standardized asymptotic confidence intervals around differences in proportions

The standardized asymptotic confidence intervals around differences in proportions are derived using the method of Miettinen and Nurminen [Miettinen, 1985].

10.2. TFL TOC

The Table Figure Listing (TFL) Table Of Content (TOC) which itemizes the planned list of TFL and their associated lay-out is developed as a separate document.

10.3. FDA toxicity grading scales for haematology/ biochemistry parameters

Serum *	Mild (Grade 1)	Moderate (Grade 2)	Severe (Grade 3)	Potentially Life Threatening (Grade 4)**
Creatinine – mg/dL	1.5 – 1.7	1.8 – 2.0	2.1 – 2.5	> 2.5 or requires
				dialysis
Liver Function Tests –ALT, AST	1.1 – 2.5 x	2.6 – 5.0 x	5.1 – 10 x ULN	> 10 x ULN
increase by factor	ULN	ULN		

* The laboratory values provided in the tables serve as guidelines and are dependent upon institutional normal parameters. Institutional normal reference ranges should be provided to demonstrate that they are appropriate.
** The clinical signs or symptoms associated with laboratory abnormalities might result in characterization of the laboratory abnormalities as Potentially Life Threatening (Grade 4). For example, a low sodium value that falls within a Grade 3 parameter (125-129 mE/L) should be recorded as a Grade 4 hyponatremia event if the subject had a new seizure associated with the low sodium value.

*** "ULN" is the upper limit of the normal range.

Hematology *	Mild (Grade 1)	Moderate (Grade 2)	Severe (Grade 3)	Potentially Life Threatening (Grade 4)
Hemoglobin (Female) - gm/dL	11.0 – 12.0	9.5 – 10.9	8.0 – 9.4	< 8.0
Hemoglobin (Female) change from baseline value - gm/dL	Any decrease – 1.5	1.6 – 2.0	2.1 – 5.0	> 5.0
Hemoglobin (Male) - gm/dL	12.5 – 13.5	10.5 – 12.4	8.5 – 10.4	< 8.5
Hemoglobin (Male) change from baseline value – gm/dL	Any decrease – 1.5	1.6 – 2.0	2.1 – 5.0	> 5.0
WBC Increase - cell/mm ³	10 800 – 15 000	15 001 – 20 000	20 001 – 25 000	> 25 000
WBC Decrease - cell/mm ³	2 500 – 3 500	1 500 – 2 499	1 000 – 1 499	< 1 000
Lymphocytes Decrease - cell/mm ³	750 – 1 000	500 – 749	250 – 499	< 250
Neutrophils Decrease - cell/mm ³	1 500 – 2 000	1 000 – 1 499	500 – 999	< 500
Eosinophils - cell/mm ³	650 – 1 500	1 501 - 5 000	> 5 000	Hypereosinophilic
Platelets Decreased - cell/mm ³	125 000 – 140 000	100 000 – 124 000	25 000 – 99 000	< 25 000

* The laboratory values provided in the tables serve as guidelines and are dependent upon institutional normal parameters. Institutional normal reference ranges should be provided to demonstrate that they are appropriate. ** "ULN" is the upper limit of the normal range.

CONFIDENTIAL 208833 (STAPH AUREUS BIOCONJ-001 STG) Statistical Analysis Plan Amendment 5

40

11. **REFERENCES**

